12.2.3 Analysis of secondary endpoints

12.2.3.1 Analysis of PFS2 endpoint

An initial PFS2 analysis will be performed at the same time as the primary analysis of PFS and will use the same methodology and model. A further analysis of PFS2 will be performed when the OS data are approximately 60% mature.

As a sensitivity, the analysis of PFS2 will be repeated in those patients whose gBRCAm status is confirmed by the central Myriad test. A KM plot of PFS2 in this subset of patients will be presented by treatment group.

The sensitivity analysis outlined for 12.2.2.1 will not be repeated for PFS2 with the exception of a Kaplan-Meier plot of the time to censoring where the censoring indicator of the primary PFS2 is reversed.

12.2.3.2 Analysis of OS endpoint

OS data will be analysed at the time of the primary analysis of PFS and will use the same methodology and model (provided there are sufficient events available for a meaningful analysis [≥ 20 deaths], if not descriptive summaries will be provided). A further interim analysis of OS will be performed when ~ 206 events are observed and a final analysis of OS will be performed when the OS data are approximately 60% mature.

An additional descriptive analysis for OS will also be performed at 7 years post the last patient randomised as part of global enrolment (DCO March 2022).

As a sensitivity, the analysis of OS will be repeated in those patients whose gBRCAm status is confirmed by the central Myriad test. A KM plot of OS in this subset of patients will be presented by treatment group.

The sensitivity analysis outlined for 12.2.2.1 will not be repeated for OS with the exception of a Kaplan-Meier plot of the time to censoring where the censoring indicator of the primary OS is reversed.

12.2.3.3 Analysis of TFST, TSST, TDT endpoints

Time to first subsequent therapy or death (TFST), time to second subsequent therapy or death (TSST) and time to study treatment discontinuation or death (TDT) will be analysed at the same time as the primary analysis of PFS and using the same methodology and model. The HRs for the treatment effect together with 95% CIs will be presented. Kaplan Meier plots will be presented by treatment arm. In addition, the time between first progression and starting first subsequent therapy will be summarised.

Summary tables of first and second subsequent therapies by treatment arm will be provided, as well as response to first and second subsequent therapy by treatment arm.

Further analyses of these endpoints will be performed at the time of each planned analysis of OS data.

As a sensitivity, the analyses of TFST, TSST and TDT will be repeated in those patients whose gBRCAm status is confirmed by the central Myriad test. KM plots of TFST, TSST and TDT in this subset of patients will be presented by treatment group.

12.2.3.4 Analysis of time to earliest progression by RECIST 1.1 or CA-125 or death

Time to progression by RECIST 1.1 or CA-125 will be performed at the same time as the primary analysis of PFS and will use the same methodology and model.

The number (%) of patients reporting a CA-125 progression, an objective RECIST 1.1 progression and both a CA-125 and/or objective RECIST progression will be tabulated.

No multiplicity adjustment will be applied as this is viewed as a supportive endpoints (to PFS).

12.2.3.5 Summary of Best overall RECIST Response (BoR)

For each treatment arm, Best Overall Response (BoR) will be summarised by n (%) for each category (CR, PR, SD, NED, PD, NE). No formal statistical analyses are planned.

The objective response rate (ORR) will be summarised (i.e., number of patients (%)) by treatment group.

12.2.3.6 Analysis of PRO endpoints

The analysis population for HRQoL data will be the subset of the FAS (ITT) set.

Change from baseline in TOI score will be regarded as the primary analysis of the FACT-O questionnaire and will be analysed using a mixed model for repeated measures (MMRM) analysis of the change from baseline in TOI score for each visit. The primary analysis will be to compare the average treatment effect from the point of randomisation for the first 24 months (which will include visit data obtained at baseline, day 29 (week 4), weeks 12, 24, 36, 48, 60, 72, 84, 96 and the discontinuation and follow-up visits if occurring within the first 24 months) unless there is excessive missing data (defined as >75% missing data). If the time to first subsequent chemotherapy when approximately 50% of placebo patients receive chemotherapy does not occur by 24 months post-randomisation then additional time periods will be analysed and will be included on supportive summaries and graphical displays as appropriate.

The MMRM model will include patient, treatment, visit and treatment by visit interaction as explanatory variables and the baseline TOI score as a covariate. Treatment, visit and treatment by visit interaction will be fixed effects in the model; patient will be included as a random effect. The treatment by visit interaction will remain in the model regardless of significance. Calculation of a suitable adjusted mean estimate will be detailed in the SAP that will estimate the average treatment effect over visits which gives each visit equal weight. The adjusted mean estimates and corresponding 95% confidence intervals will be presented for the overall treatment comparison and by visit for each treatment group.

Date 05 November 2021

Descriptive statistics and graphs will be reported for the TOI by visits as well as change in these scores from baseline. These will also be reported for the physical well being (PWB), social well being (SWB), emotional well being (EWB), functional well being (FWB) and the ovarian cancer subscale (Additional Concerns) domains.

Summary tables of Trial Outcome Index (TOI) best change rates will be provided.

12.2.3.7 Health State Utility – EQ-5D-5L

Descriptive statistics will be reported for EQ-5D-5L health state utility values and the visual analogue score by visit, as well as change in these scores from baseline. Further details of the exploratory analysis will be outlined in the statistical analysis plan (SAP).

The scores for each of the EQ-5D-5L health state utility values and visual analogue will be summarised in terms of mean changes from baseline at each post-baseline assessment (with n, standard deviation, min, max presented). If less than 50% of the items in one health state are missing, the mean scores for the completed items will be used for imputation. If 50% or more of the items in one health state are missing, that subscale will be treated as missing.

12.2.3.8 Impact of Switching to PARP inhibitors (or other potentially active investigational agents) on Overall Survival Analyses

Exploratory analyses of OS adjusting for impact of subsequent PARP inhibitor trial or treatment may be performed if a sufficient proportion of patients switch. Methods such as Rank Preserving Structural Failure Time (RPSFT) (Robins et al 1991), Inverse Probability of Censoring Weighting (IPCW) (Robins 1993) and other methods in development will be explored. The decision to adjust and final choice of methods will be based on a blinded review of the data and the plausibility of the underlying assumptions. Baseline and time-dependent characteristics will be explored, and summaries of baseline characteristics will be summarised for placebo patients, splitting between those that have and haven't switched at the time of the analyses. Further detail will be provided in the SAP and Payer Analysis Plan.

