6.5.4 EQ-5D-5L

Patient reported health state utility will be assessed using the EQ-5D-5L. The instrument asks patients to respond to 5 different dimensions covering mobility, self-care, usual activities, pain/discomfort, anxiety/ depression, as well as rate how they feel on the day of assessment via a visual analogue scale.

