3.3.2 EQ-5D-5L (exploratory analysis)

The EQ-5D-5L, developed by the EuroQol Group, is a generic questionnaire that provides a simple descriptive profile and a single index value for health status for economic appraisal. The questionnaire comprises six questions that cover five dimensions of health (mobility, self-care, usual activities, pain/discomfort and anxiety/depression) and how the patient feels. For each dimension, patients select which statement best describes their health on that day from a possible five options of increasing levels of severity (no problems, slight problems, moderate problems, severe problems and unable to/ extreme problems). A visual analogue scale (VAS) which ranges from 0 (worst imaginable health) to 100 (best imaginable health) is used to assess how the patient feels.

The EQ-5D-5L index comprises six questions that cover five dimensions of health (mobility, self-care, usual activities, pain/discomfort and anxiety/depression) and a VAS. A unique health state, the EQ-5D-5L profile, based on the five dimensions is reported as a five-digit code with a possible total of 3,125 health state. For example, state 11111 indicates no problems on any of the five dimensions. This EQ-5D-5L profile will be converted into a weighted health state utility value, termed the EQ-5D index, by applying a country-specific equation to the profile that represents the comparative value of health states. This equation is based on national valuation sets elicited from the general population and the base case will be the UK perspective. Where a valuation set has not been published, the EQ-5D-5L profile will be converted to the EQ-5D index using a crosswalk algorithm (van Hout et al 2012). The visual analogue scale, the EQ-VAS, is reported separately.

The evaluable population will comprise the FAS population.

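### The protocol's EQ-5D-5L rule fills a missing dimension with the mean of the others, which borrows across unrelated dimensions and can give a level outside the SAP's 3,125 profiles

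*Protocol*

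**What the plan says.** Protocol 6.5.4 describes the instrument: "The instrument asks patients to respond to 5 different dimensions covering mobility, self-care, usual activities, pain/discomfort, anxiety/ depression", plus a visual analogue scale (VAS). SAP 3.3.2 adds that for each dimension "patients select which statement best describes their health on that day from a possible five options of increasing levels of severity". The five answers form a profile that "is reported as a five-digit code with a possible total of 3,125 health state". The index is then obtained "by applying a country-specific equation to the profile that represents the comparative value of health states", or by a crosswalk where no value set has been published.

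Protocol 12.2.3.7 gives the missing-data rule in two sentences. The first covers a health state with fewer than half of its items missing: "the mean scores for the completed items will be used for imputation". The second: "If 50% or more of the items in one health state are missing, that subscale will be treated as missing". The same section leaves further detail of the exploratory analysis to the SAP.

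Neither SAP 3.3.2 nor SAP 4.2.10 contains a rule for missing EQ-5D-5L items. SAP section 6, which lists departures from the protocol, does not mention the topic. The SAP's only 50% rule is in 3.3.1, for the FACT-O subscales.

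**The concern.** The rule has the form of a half-rule for a summed scale. Prorating makes sense for FACT-O because each subscale adds up several items on one theme, so the completed items carry information about the missing one. The EQ-5D-5L has no such subscale in either document, although the second sentence of the rule uses that word. Each dimension is one question on its own subject, so the rule would fill anxiety from mobility and self-care, or pain from usual activities.

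A second problem follows from the SAP's own definition. The index is a function of a code made of five whole levels. A mean of several levels need not be a whole level, and the visible text does not say what to do when it is not. A programmer would have to choose a rounding rule, feed a fractional level into the value-set equation, or depart from the protocol without recording it.

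What is at stake is the utility index on partly completed forms. It feeds the by-visit and change-from-baseline summaries in Protocol 12.2.3.7 and SAP 4.2.10, and the economic use that the protocol synopsis and SAP 4.2.10 anticipate.

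**Working it through.** **Inputs.** Five dimensions (Protocol 6.5.4); five ordered levels per dimension and 3,125 profiles (SAP 3.3.2); imputation when fewer than 50% of the items in one health state are missing (Protocol 12.2.3.7). The items of one health state are read as its five dimensions, which is the natural reading because the state is defined by them.

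**The plan's own figure.** 5 levels to the power of 5 dimensions = 5^5 = 3,125. This reproduces SAP 3.3.2 and confirms that only whole levels 1 to 5 are admitted.

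**When the rule applies.** 1 missing: 1/5 = 20%, impute. 2 missing: 2/5 = 40%, impute. 3 missing: 3/5 = 60%, treat as missing.

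**What it produces.**
- Completed 1, 1, 2, 5: (1+1+2+5)/4 = 9/4 = 2.25
- Completed 1, 1, 1, 2: 5/4 = 1.25
- Completed 1, 1, 2: 4/3 = 1.33
- Completed 1, 1, 1, 1: 4/4 = 1

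The first three are not digits of a five-digit code, so the resulting profiles are not among the 3,125. The fourth can be valued, but its level still comes from other dimensions.

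**Share of possible patterns.** All completed patterns were listed, and the mean is whole when the sum divides evenly.
- One missing: 5^4 = 625 patterns, of which 157 give a whole level. Non-integer: 625 − 157 = 468, and 468/625 = 74.9%.
- Two missing: 5^3 = 125 patterns, of which 41 give a whole level. Non-integer: 125 − 41 = 84, and 84/125 = 67.2%.

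These are shares of patterns treated as equally likely, not expected shares of patients.

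**Sensitivity to the answers given.** The documents report no distribution of levels, so the following are assumptions, with dimensions taken as independent.

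| Assumed % at levels 1/2/3/4/5 | Non-integer, 1 missing | Non-integer, 2 missing |
|---|---|---|
| 90/8/2/0/0 | 34.1% | 26.2% |
| 80/15/4/1/0 | 56.4% | 43.6% |
| 60/25/10/4/1 | 74.2% | 61.9% |
| 40/30/20/8/2 | 75.4% | 66.4% |

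**After the fix.** If the index is set to missing whenever a dimension is missing, every valued profile has five observed whole levels, so none falls outside the 3,125.

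**The case against.** The strongest reply is that little remains to correct. Protocol 6.5 says these questionnaires are no longer collected after the primary analysis, and SAP section 5 shows that the primary analysis has passed. The EQ-5D-5L is exploratory and summarised descriptively; it is not in the SAP's Table 7 of formal analyses or in the multiple testing procedure. Protocol 6.5.1 has staff check returned forms for completeness, so partly completed forms may be rare. SAP 4.2.10 already reports, by visit and arm, the questionnaires completed and the numbers answering each dimension, and SAP 3.3.2 already reports the VAS separately. All of this stands and limits the size of the point.

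The text of Protocol 11.3.1, which the contents list as the EQ-5D-5L derivation, is redacted, so a rounding rule may exist there. That also stands, and the absence of visible text is not evidence that the plan lacks one. Rounding would restore a valid code, but it would not answer the objection to filling one dimension from others.

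It could also be argued that the SAP's silence replaces the rule. It does not: SAP section 6 is where a change would be declared, and it declares none.

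A reader might infer that imputed states in general cannot be valued, or that the mean is usually fractional. The documents do not support either. Some patterns give whole levels, and if 90% of answers are at level 1 the fractional results are a minority.

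**Conclusion.** The point holds in a limited form. The rule in Protocol 12.2.3.7 does not fit the instrument as the two documents describe it. Whenever it is applied, it assigns a level taken from unrelated dimensions; in some cases it also gives a level that SAP 3.3.2 cannot turn into an index without a further step that is not visible.

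The size is small. Under the assumed distributions, the non-integer share of imputations is about 34% to 75% with one dimension missing and 26% to 66% with two. The number of partly completed forms is not given, so the number of affected utility values cannot be stated. The cross-dimension borrowing does not depend on those assumptions.

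The effect is confined to exploratory descriptive utility summaries and later economic re-use of data already collected. No primary or key secondary result changes. A reader might also infer that utility values already reported are wrong; the documents do not show how incomplete forms were actually handled, so that does not follow.

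**What to change.** Delete the two imputation sentences in Protocol 12.2.3.7. State in SAP 3.3.2 that the EQ-5D-5L index is missing when any of the five dimensions is missing, and that the VAS is summarised as observed. List this in SAP section 6 as a change from the protocol. If Protocol 11.3.1 contains a missing-item or rounding rule, bring it into line. No new table of incomplete forms is needed, since SAP 4.2.10 already covers most of that information.

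The change is to wording and to one derivation step; it needs no new data. The downside is a few more missing index values, and the tables in SAP 4.2.10 would help to show how many. If payer work needs values for those forms, any imputation should be at the level of the index and specified in the Payer Analysis Plan.

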12.2.4 Exploratory endpoints

Exploratory endpoints are covered by PRO endpoints. For analysis description please see Section 12.2.3.6.

12.2.5 Interim analyses

No interim analyses of PFS prior to the primary analysis will be performed, however additional summaries of PFS or other variables (efficacy or safety) may be performed to meet Regulatory Agency requests.

[REDACTED]
Date 05 November 2021

[REDACTED]

12.3 Determination of sample size

The sample size for this study was selected to be consistent with the research hypothesis as described in Section 1.

The primary endpoint of the study is PFS.

In total 206 PFS events in the study would have 90% power to show statistically significant PFS at the 2-sided 5% level if the assumed true treatment effect were HR 0.62; this translates to a 8 month benefit in median PFS over 13 months on placebo (estimated from data reported by [Alsop et al 2012](#)) if PFS is exponentially distributed.

Approximately 344 patients will be recruited (2:1 ratio) so that data maturity for the PFS analysis is approximately 60%. When global enrolment closed on 14 November 2014, patients still in screening were permitted to be randomised and therefore a total of 391 patients were randomised as part of Global recruitment.

Assuming 18 months non-linear recruitment, 206 PFS events are expected to occur approximately 36 months after first subject in is enrolled in the study (FSI). This will be the primary analysis of PFS. No further analyses of PFS are planned beyond this point unless requested by Health Authorities.

At this time, an interim analysis of OS will also be performed. It is anticipated that approximately 100 OS events (29% maturity) will have occurred. Assuming that the true OS treatment effect is 0.85 and if this point estimate for the HR of 0.85 was observed, the 95% upper confidence limit (UCL) for the HR would be 1.29.

A further interim analysis of OS may be performed at approximately 206 events. Assuming that the true OS treatment effect is 0.85 and this point estimate for the HR of 0.85 was observed, the 95% UCL for the HR would be 1.13. A final OS analysis may be performed at approximately 60% maturity (~235 events/391 patients who were randomised in SOLO1). Assuming that the true OS treatment effect is 0.85 and this point estimate for the HR of 0.85 was observed, the 95% UCL for the HR would be 1.11. Note that these estimates are based on the assumption that no confounding will occur. AstraZeneca anticipates potential confounding of OS data due to availability of PARP inhibitors for BRCA mutated ovarian cancer patients during follow up in this study, which are likely to disproportionately affect OS in one arm of the study (placebo-treated patients).

Pharmacogenetic research (PGx) The number of patients that will agree to participate in the genetic research is unknown. It is therefore not possible to establish whether sufficient data will be collected to allow a formal statistical evaluation or whether only descriptive statistics will be generated. A statistical analysis plan will be prepared where appropriate.

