6.2.7 Patient management post primary analysis

The data cut off date for the statistical analysis for the primary objective of the study will be established when approximately 196 confirmed progression events have occurred or after the last patient randomised has had the opportunity to have been on the study for at least 36 months, whichever comes first.

Patients on study treatment at the time of the data cut-off will continue to receive study treatment until they meet any discontinuation criteria as per Section 5.8.

Patients on study treatment will be followed for core safety assessments and disease progression (haematology, clinical chemistry, AEs/SAEs and concomitant medications (including any subsequent cancer therapy), study treatment dosing details, objective radiological disease progression according to RECIST, as per Table 3). These patients should be followed according to routine clinical practice but visits should take place at least every 12 weeks (see Table 3).

All patients (patients still on study treatment and patients withdrawn from study treatment) will be followed for survival and disease progression.

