12.2.2 Analysis of primary endpoint

PFS will be analysed when approximately 196 events have occurred or after the last patient randomised has had the opportunity to have been on the study for at least 36 months, whichever comes first. No further analyses of PFS are planned beyond this point unless requested by Health Authorities.

PFS will be analysed using a log rank test stratified by response to first line platinum chemotherapy (clinical complete response partial response) for generation of the p-value and using the Breslow approach for handling ties. The hazard ratio (HR) and confidence interval will be estimated from a Cox Proportional Hazards model (with ties = Efron and the stratification variable as a covariate) and the CI will be calculated using a profile likelihood approach.

Stratification variables will be defined according to data from the interactive voice/web response system (IVRS/IWRS). If there are any patients who were mis-stratified, a sensitivity analysis will be carried out using the (correct) baseline data collected in the eCRF.

The HR (olaparib vs placebo) together with its corresponding 95% confidence interval (CI) and p-value will be presented (a HR less than 1 will favour olaparib).

A Kaplan-Meier (KM) plot of PFS will be presented by treatment group. Summaries of the number and percentage of subjects experiencing a PFS event, and the type of event (RECIST or death) will be provided along with median PFS for each treatment.

The assumption of proportionality will be assessed. Note that in the presence of non-proportionality, the HR will be interpreted as an average HR over the observed extent of follow-up. Proportionality will be tested firstly by examining plots of complementary log-log (event times) versus log (time) and, if these raise concerns, a time dependent covariate would be fitted to assess the extent to which this represents random variation.

The primary analysis will be based on the programmatically derived PFS based on Investigator recorded assessments, and using all scans regardless of whether they were scheduled or not.

The proportion of patients alive and progression free at 6 months and 12 months will be summarised (using the KM curve) and presented by treatment group.

Date 05 November 2021

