1.3 Number of Subjects

In total 206 PFS events in the study would have 90% power to show statistically significant PFS at the 2-sided 5% level if the assumed true treatment effect were hazard ratio (HR) 0.62; this translates to a 8 month benefit in median PFS over 13 months on placebo (estimated from data reported by Alsop et al 2012) if PFS is exponentially distributed.

Approximately 344 patients will be recruited (2:1 ratio) so that data maturity for the PFS analysis is approximately 60%. When global enrolment closed on 14 November 2014, patients still in screening were permitted to be randomised and therefore a total of 391 patients were randomised as part of Global recruitment.

Assuming 18 months non-linear recruitment, 206 PFS events are expected to occur approximately 36 months after first subject in is enrolled in the study (FSI). At this time, an interim analysis of OS will also be performed.

PFS will be analysed when approximately 196 events have occurred or after the last patient randomised has had the opportunity to have been on the study for at least 36 months, whichever comes first. No further analyses of PFS are planned beyond this point unless requested by Health Authorities.

A further interim analysis of OS may be performed at approximately 206 events (~53% maturity of the 391 patients randomised). Assuming that the true OS treatment effect is 0.85 and this point estimate for the HR of 0.85 was observed, the 95% UCL for the HR would be 1.13. A final OS analysis may be performed at approximately 60% maturity (~235 events/391 patients who were randomised in SOLO1). Assuming that the true OS treatment effect is 0.85 and this point estimate for the HR of 0.85 was observed, the 95% UCL for the HR would be 1.11. Note that these estimates are based on the assumption that no confounding will occur. AstraZeneca considers there will be potential confounding of OS data due to availability of PARP inhibitors for BRCA mutated ovarian cancer patients during follow up in this study, which are likely to disproportionately affect OS in one arm of the study (placebo-treated patients).

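### Protocol 12.3 and the synopsis still name 206 events in 344 patients as the primary PFS analysis, but the operative trigger is about 196 events (or 36 months) in 391 patients: about 88% power and 50% maturity, not 90% and 60%

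*Protocol*

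**What the plan says.** **Design basis.** Protocol 12.3 says "In total 206 PFS events in the study would have 90% power to show statistically significant PFS at the 2-sided 5% level". The effect behind this is a hazard ratio of 0.62, that is, a median of 21 months against 13 on placebo. On recruitment and maturity it says: "Approximately 344 patients will be recruited (2:1 ratio) so that data maturity for the PFS analysis is approximately 60" per cent. On timing, "206 PFS events are expected to occur approximately 36 months after first subject in", and the next sentence calls this the primary PFS analysis. The same paragraph rules out later PFS analyses beyond that point, and the following one places an OS interim at that time. The synopsis repeats the 206-event forecast and also names it the primary analysis. SAP 1.3 repeats the basis ("In total 206 PFS events in the study would have 90% power"). It does not call 206 events the primary analysis, but it does place the OS interim at the 206-event time.

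**Operative trigger.** Protocol 12.2.2 says "PFS will be analysed when approximately 196 events have occurred", or once the last patient randomised has had the opportunity for at least 36 months on study, whichever comes first. The synopsis methods, protocol 3.1, SAP 1.3 and SAP 4 give the same rule. Protocol 6.2.7 gives it too, but counts "approximately 196 confirmed progression events have occurred".

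**Denominator.** Protocol 12.3, the synopsis and SAP 1.3 report 391 patients randomised in global enrolment. Protocol 12.1.1 puts all of them in the full analysis set. Nowhere is power or PFS maturity restated for 196 events in 391 patients.

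**The concern.** Someone who reads only protocol 12.3 would expect the primary analysis at 206 events and 60% maturity. Someone who reads 12.2.2 would expect it at about 196 events. The synopsis contains both. These are the documents against which pre-specification of the primary analysis is judged, so on the first reading an analysis at 196 events looks ten events early.

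The trigger also fixes other looks. Protocol 12.2.1 times the PFS2 interim and the first OS interim to the PFS analysis, and both belong to the alpha-controlled procedure. SAP 1.3 ties the OS interim to the 206-event time, whereas SAP 4.2.1 ties it to the PFS analysis.

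Protocol 6.2.7 adds a third form of words. Read literally, its count omits deaths, although PFS includes death from any cause (protocol 11.1.1, SAP 3.2.1).

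**Working it through.** **Inputs.** HR 0.62, two-sided 5%, 90% power, 206 events, 2:1 allocation and 344 planned patients (protocol 12.3). Trigger of 196 events (protocol 12.2.2). 391 patients randomised (protocol 12.3), all in the full analysis set (protocol 12.1.1).

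**1. Reproduce the plan's figures** (Schoenfeld; the 2:1 factor is 2/3 × 1/3 = 2/9)

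- Events for 90% power = (1.960 + 1.282)² / [(ln 0.62)² × 2/9] = 206.9. With HR = 13/21 = 0.619, the result is 206 after rounding up.
- Power at d events = Φ(|ln 0.62| × √(2d/9) − 1.960).
- d = 206: Φ(0.478 × 6.766 − 1.960) = 89.9%.
- Maturity = 206/344 = 59.9%.

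The stated 206, 90% and 60% therefore agree with one another for 344 patients.

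**2. The operative event branch**

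- d = 196: Φ(0.478 × 6.600 − 1.960) = 88.4% (88.6% with HR = 13/21).
- Maturity = 196/391 = 50.1%.

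| Design | Power at HR 0.62 | Maturity |
|---|---|---|
| 206 of 344 (stated) | 89.9% | 59.9% |
| 206 of 391 | 89.9% | 52.7% |
| 196 of 391 (operative) | 88.4% | 50.1% |
| 235 of 391 | 93.2% | 60.1% |

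Most of the fall in maturity comes from the larger denominator; the lower event count adds 2.6 points. In 391 patients no single event count gives both 90% power and 60% maturity.

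**3. Could the 36-month branch come first under the design's own inputs?** Take exponential PFS with medians 13 and 21 months, 391 patients, exactly 36 months' follow-up for everyone (the minimum) and no dropout:

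- 391 × [2/3 × (1 − 2^(−36/21)) + 1/3 × (1 − 2^(−36/13))] = 391 × [2/3 × 0.695 + 1/3 × 0.853] ≈ 292 events.

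That is well above 196, so under these inputs the event branch applies.

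**4. OS figures affected by the same change**

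- Protocol 12.3 gives about 100 OS events as 29% maturity. 100/344 = 29.1%, but 100/391 = 25.6%. The same section uses 391 for the final OS analysis (235/391 = 60.1%).
- Upper limit for an observed HR of 0.85 = 0.85 × exp(1.96/√(2d/9)). At 100 events it is 1.288 (stated 1.29), at 235 it is 1.115 (stated 1.11), and at 206 it is 1.136 (stated 1.13 in protocol 12.3 and SAP 1.3; it rounds to 1.14).

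**The case against.** **The analysis is over.** SAP section 5 refers to events after the PFS analysis in the past tense, and protocol 6.5 says PRO collection stopped because the study is past its primary analysis. Planned power does not alter a completed test. This stands, and it limits the point to the record.

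**The quoted sentence is correct.** 206 events do give 90% power at HR 0.62 with 2:1 allocation, and the shortfall at 196 is about 1.6 points, with both triggers worded as approximate. This stands. A reader might infer that the sample size was miscalculated or the trial materially underpowered; the arithmetic supports neither.

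**The SAP mostly copes.** SAP 1.3 keeps 206 as the design basis and then states the 196-event trigger. That is largely right, but its OS interim sentence is still attached to 206 events, and it gives no power or maturity for 196 of 391.

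**The two 36-month periods do not compete.** In 12.3 the period is a forecast from first enrolment; in 12.2.2 it is a time limit from the last randomisation. This is fair. The conflict lies in the sentence that makes the forecast point the primary analysis.

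**The time branch.** A reader might infer that it could have forced the analysis at far fewer events and much lower power. The documents give no such count, and the design's own medians give about 292 events by then without dropout, so no criticism of that branch is made here.

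**Protocol 6.2.7 is loose wording.** Probably so, since PFS is defined to include death and the other trigger statements simply say events. It is still worth aligning.

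**Conclusion.** The inconsistency is real and sits in the current text. Protocol 12.3 and the synopsis name 206 events as the primary PFS analysis, against a rule of about 196 events or 36 months in the synopsis methods, protocol 3.1, 6.2.7 and 12.2.2, and SAP 1.3 and 4. On the event branch the plan has about 88.4% power rather than 90%, and 50.1% maturity rather than 60%. The trigger and the maturity matter more than the power.

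The figures assume HR 0.62, two-sided 5%, 2:1 allocation, the Schoenfeld approximation and 391 patients as denominator. They apply only if the 196-event branch sets the cut-off.

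A reader might infer that the primary analysis departed from its plan or that the PFS result is weakened. The documents do not support that: the analysis section of the protocol and the SAP agree on 196 events or 36 months, and the 206-event statement is text left over from the 344-patient design.

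**What to change.** **Protocol 12.3 and the synopsis**

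- Keep 206 events in 344 patients, 90% power and 60% maturity, labelled as the original design basis.
- Delete the sentence after the 206-event forecast that calls it the primary PFS analysis.
- State that the primary analysis occurs at about 196 PFS events (progression or death), or when the last patient randomised has had at least 36 months on study, whichever comes first. Add that, if the event branch applies, power is about 88% at HR 0.62 and maturity about 50% (196/391).
- In 12.3, re-attach to that trigger the statement that no further PFS analyses are planned and the statement placing the OS interim.

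**SAP 1.3**

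- Re-attach the OS interim sentence to the same trigger and add the power and maturity for 196 of 391.

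**Protocol 6.2.7**

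- Replace the reference to confirmed progression events with PFS events.

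**Minor, in the same edit**

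- In protocol 12.3, express about 100 OS events as about 26% of 391.
- In protocol 12.3 and SAP 1.3, correct the OS upper limit at 206 events from 1.13 to 1.14.

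The cost is wording only. The stated power and maturity become slightly less favourable. No analysis changes.
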